**LIST OF ABBREVIATIONS**

Abbreviation	Definition
ACE-2	angiotensin converting enzyme 2
ADE	antibody-mediated disease enhancement
AE	adverse event
AESI	adverse event of special interest
ALP	alkaline phosphatase
ALT	alanine aminotransferase
API	active pharmaceutical ingredient
AST	aspartate aminotransferase
BMI	body mass index
CBER	Center for Biologics Evaluation and Research
CDC	Centers for Disease Control and Prevention
CD4+	white blood cell T helper cell subtype
CD8+	white blood cell T cytotoxic cell subtype
CFR	Code of Federal Regulations
cGMP	current Good Manufacturing Practice
CI	confidence interval
CoV	coronavirus
CpG	Cytosine PhosphoGuanine
CPMP	Committee for Proprietary Medicinal Products
CRA	clinical research associate
CRU	clinical research unit
CRO	contract research organization
CSR	clinical study report
CV%	coefficient of variation (percentage)
DAIDS	Division of AIDS
DILI	drug-induced liver injury
DNA	deoxyribonucleic acid
ECG	electrocardiogram
ECMO	extracorporeal membrane oxygenation
eCRF	electronic case report form
ELISA	enzyme-linked immunosorbent assay
EOS	end-of-study
Fc $\gamma$ RII	Fc gamma region II of IgG
FDA	Food and Drug Administration
FIH	first-in-human
FiO 2	fraction of inspired oxygen
FSH	follicle-stimulating hormone
GeoCV%	geometric coefficient of variation (percentage)
GGT	gamma-glutamyl transferase
GMFR	geometric mean fold rise
GMI	geometric mean increase
GMT	geometric mean titer
H1N1	influenza A virus subtype H1N1
H3N2	influenza A virus subtype H3N2

Abbreviation	Definition
HBsAg	hepatitis B surface antigen
HCV	hepatitis C virus
HIPAA	Health Insurance Portability and Accountability Act of 1996
HIV	human immunodeficiency virus
ICD	International Classification of Diseases
ICF	informed consent form
ICU	intensive care unit
Ig	immunoglobulin
IL	interleukin
IM	intramuscular
IRB	institutional review board
IFN- $\gamma$	interferon gamma
iSRC	independent safety review committee
KBP	Kentucky BioProcessing, Inc.
MAAE	medically attended adverse event
MedDRA	Medical Dictionary for Regulatory Activities
MERS-CoV	Middle East Respiratory Syndrome coronavirus
mITT	Modified Intent-to-Treat Population
NOCD	new onset chronic disease
PaO 2	partial pressure of oxygen
PBMC	peripheral blood mononuclear cell
PE	physical examination
PP	Per Protocol
RBD	receptor binding domain
RBD-Fc	fusion protein containing RBD fused to the Fc domain of a human IgG1
RT-PCR	reverse transcription polymerase chain reaction
SAE	serious adverse event
SAP	Statistical Analysis Plan
SOP	standard operating procedure
SpO 2	oxygen saturation
SRM	study reference manual
SSP	study-specific procedure
TAP	Tobacco Mosaic Virus Antigen Presentation
TAP-COVID-19	Tobacco Mosaic Virus Antigen Presentation SARS-CoV-2 virus Receptor Binding Domain fused to Fc Domain
TEAE	treatment-emergent adverse event
TLR9	Toll-like Receptor 9
TMV	Tobacco Mosaic Virus
ULN	upper limit of normal
US or USA	United States of America
VS	vital signs
WHO	World Health Organization
WOCBP	Women of childbearing potential

## **2 INTRODUCTION AND BACKGROUND**

### **2.1 Introduction**

To date, seven CoVs capable of human infection have been identified, including SARS-CoV, MERS-CoV, and a newly identified CoV (SARS-CoV-2). These 3 viruses, when in the human population, are significant public health risks showing high fatality rates: SARS-CoV = 10%, MERS-CoV = 34.4% and SARS-CoV-2 = 6.1%. The SARS-CoV-2 virus has spread to >180 countries since December 2019, infected >5.7 million humans, and been attributed to >350,000 deaths worldwide [John Hopkins 2020]. These numbers are growing exponentially, creating worldwide health and economic crises. The emergence of this disease and its effects on human health and economic security demands urgent response.

TAP-COVID-19 Vaccine is being developed for the prevention of SARS-CoV-2 infection in healthy adults aged 18 and older. For this Phase 1 Study, the TAP-COVID-19 vaccine will be evaluated with a CpG adjuvant based on preclinical studies showing it provides a Th1 biased immune response against SARS-CoV-2.

### **2.2 Study Vaccine Background**

#### **2.2.1 Receptor Binding Domain Vaccine Strategy**

Focusing CoV vaccine efforts around the RBD (S1 domain) of the spike glycoprotein have produced encouraging outcomes. SARS-CoV RBD has been shown to bind the human receptor for ACE-2, contains multiple conformation-dependent epitopes that can elicit high-titer neutralizing antibodies [Wang 2020; Kam 2007; Jaume 2012; Quinlan 2020]. Most relevant to the KBP vaccine strategy, *in vivo* studies showed that a fusion protein containing RBD-Fc elicited high levels of neutralizing antibodies against SARS-CoV in both immunized rabbits and mice. These antibodies blocked spike interaction with the human receptor ACE-2. Most interestingly, the RBD-Fc protein induced long lasting, potent neutralizing antibody titers maintained for 12 months after immunization – even protecting most vaccinated mice from SARS-CoV challenge [Du 2007; Du 2009]. Importantly, many different versions of SARS or MERS-RBD vaccines have been developed and tested, alone and with adjuvant, produced in mammalian cells, and insect cells and plants. All have shown protection from infection through virus neutralization without accompanying immunopathology associated with full-length or trimerized S protein vaccines [Wang 2020; Kam 2007; Jaume 2012; Quinlan 2020].

#### **2.2.2 TAP-COVID-19 Vaccine – A Novel Vaccine for COVID-19 Disease Prevention**

Based on the prior experience with Coronavirus family viruses described above, KBP has developed the RBD-Fc antigen linked to its novel TAP platform to accelerate development of an effective and scalable vaccination strategy. The KBP platform combines the well-established speed and robustness of its transient Nicotiana benthamiana gene expression system with the immune stimulation effects of antigen-association with the inactivated TMV virus structure. Using standardized gene expression and downstream processing strategies, while maintaining a warm

base of naïve plants, the TAP platform has the potential to rapidly deliver vaccines with significant production potential of millions of doses of vaccine API per month.

Historical preclinical data illustrates the ability of TAP vaccines to provide balanced humoral and cellular responses in mammals allowing efficacious responses to be generated against a wide range of pathogens with different immune correlates of protection [McCormick 2006a; McCormick 2006b; Banik 2015; Arnaboldi 2016; Mallajosyula 2016; Mallajosyula 2014].

The TAP vaccine system offers key advantages of:

- Speed: <10 weeks from sequence to cGMP vaccine
- Balanced immune response: effective stimulation of both Th1 and Th2 arms of the immune system
- Stability: showing room temperature shelf life past 6-months at room temperature with no loss of potency
- Scalability: potential to deliver millions of doses of vaccine API per month
- Robustness: showing safety in murine, ferret, and rabbit preclinical models and efficacy against challenge with seven viruses and three bacterial pathogens, including human influenza virus, *Yersinia pestis*, *Francisella tularensis*, and *Mycobacterium tuberculosis*

### **2.2.3 CpG Adjuvant**

The TAP-COVID-19 Vaccine will be combined with CpG 7909 adjuvant. CpG 7909 is a short (24 nucleotide) synthetic form of DNA that mimics bacterial and viral genetic material that, when included into a vaccine, increases the body's immune response through engagement of TLR9 within antigen presenting dendritic cells and B cells. TLR9-engaging adjuvants are known to generate Th1 cell- and cytokine-mediated immune responses (IFN- $\gamma$  and IL-2) generated by Th1 cells and IgG2a isotype antibodies and to vaccine antigens and pathogens. Generation of a Th1-biased humoral response may reduce risk associated with antibody-mediated disease enhancement based on Fc $\gamma$ RII receptor affinity for Th1 antibodies versus Th2 antibodies [de Alwis 2020; Fierz 2020].

### **2.2.4 Data Supporting Development of TAP-COVID-19 Vaccine**

#### **2.2.4.1 Binding to CR3022 Monoclonal Antibodies**

Preliminary data indicates the RBD-Fc intact antigen binds to the human ACE-2 receptor and a SARS-CoV-2 RBD-specific, human neutralizing monoclonal antibody, CR3022. The data shows strong, dose-dependent binding of CR3022 to RBD-Fc antigen and RBD-Fc TAP vaccine. The RBD-Fc candidate antigens show >5X reactivity to CR3022 compared with commercially sourced control SARS spike and RBD reagents. These data suggest that the purified SARS-CoV-2 RBD-Fc antigen maintains essential conformational epitopes in a manner superior to commercially purchased reagents.

#### **2.2.4.2 Binding to ACE-2 Receptor**

Recombinant ACE-2 complexes containing RBD-Fc can be immunoprecipitated by ACE-2 specific antisera in vitro. However, this does not provide a quantitative measure of binding. Quantitative and functional ACE-2 binding was performed using confocal microscopy and analysis by co-localization and competitive binding methods on Vero e6 cells in collaboration with scientists at the University of Louisville, Center for Predictive Medicine and Department of Microbiology & Immunology. The ability of the native agonist, angiotensin II, was compared with the RBD-Fc fusion or concentration dependent ability to block binding of an ACE-2 specific antibody to the receptor on living cells. Influenza H7 hemagglutinin was used as a control. FAM-angiotensin II bound to Vero e6 cells, with an average of a 2.79-fold increase over the non-specific H7 control.

Binding of the RBD-Fc antigen to Vero e6 cells occurred in a concentration-dependent manner with an increase of 2.58-fold increase over the H7 control. Binding of H7 did not impact detection of ACE-2 by monoclonal antibody at any concentration.

SARS-CoV-2 RBD-Fc fusion antigen shows functional conformation and activity through the binding by CR3022 and ACE-2. Binding to ACE-2 shows similar affinity and specificity as angiotensin II suggesting that the conformation of the spike protein RBD in the antigen-antibody complex is comparable to that observed with native SARS-CoV-2 spike protein. The data suggests that both antigen-antibody complexes display the correct structure necessary to elicit neutralizing antibodies to the RBD of SARS-CoV-2 spike protein.

### **2.3 Summary of Findings to Date**

KBP is also actively developing a quadrivalent seasonal influenza vaccine, TAP-V001, using the TAP platform. Nonclinical studies performed to support TAP-V001 are relevant and supportive of the TAP-COVID-19 program based on the quantities of the vaccine components. In particular, IND-enabling pharmacokinetic/biodistribution and GLP repeat dose toxicology studies have been completed using two different formulations of TAP-V001 vaccine that demonstrated:

- No observed treatment-related or toxicologically significant clinical findings or inoculation site reactogenicity
- No observed treatment-related or toxicologically significant effects for body weights, body weight changes, food consumption, body temperatures, ophthalmology, clinical chemistry, hematology, organ weights, and gross and microscopic pathology
- Dose dependent TMV-specific RT-PCR signal measured at site of injection with rapid clearance from all non-target organs
- Maintenance of TMV-specific RT-PCR signal in immune-processing organs, including lymph nodes and spleen
- Efficacy in two ferret challenge studies, revealing statistically improved H1N1 clearance and statistically equivalent H3N2 clearance compared with Fluzone® control.

The same platform manufacturing process for production of TAP-V001 is used in the production of TAP-COVID-19, with the exception of the affinity chromatography resin, and a similar drug product formulation is employed.

## **2.4 Study Rationale**

Multiple vaccines have been approved for emergency use for the prevention of SARS-CoV-2, with other vaccines close to being available either through emergency use or licensed vaccines. Although work continues on antiviral treatments for SARS-CoV-2, given the crisis of COVID-19 infections in the world, the fast expansion to the US and other parts of the world, and the global push to vaccinate everyone, additional sources of effective vaccine will be needed.

## **2.5 Dose Rationale**

As SARS-CoV-2 is a newly emergent respiratory viral disease, naïve subjects are expected to require a two dose (prime-boost) immunization regimen to generate a suitable immune response to offer protection from infection. The TAP-COVID-19 vaccine dose levels to be evaluated have been established using a prime-boost dosing strategy in mice as a model species to characterize the vaccine's immunogenicity. Two doses of TAP-COVID-19 have demonstrated a robust and dose-dependent increase in the humoral antibody response to the vaccine in both total antibody and neutralizing antibody titers. This response was seen in separate KBP studies conducted at two different academic centers.

The selected regimen is anticipated to be safe based on nonclinical toxicology studies conducted in rabbits which employed a 4-fold higher antigenic dose levels of a quadrivalent influenza vaccine candidate. There were no toxicologically relevant findings and it was determined that a property of TAP-based vaccines is the trafficking to immune organs (draining lymph nodes and spleen) which may serve as a mechanism for driving the immune response.

Lastly, the proposed rationale for dose level and the dosing regimen is based on historical experience with other pandemic respiratory viral diseases including influenza and prior coronavirus outbreaks and is also consistent with other ongoing SARS-CoV-2 clinical studies.

### **3 OBJECTIVES AND ENDPOINTS**

#### **3.1 Objectives**

##### **3.1.1 Primary Objective**

To assess the safety and reactogenicity of two doses of TAP-COVID-19 vaccine with CpG adjuvant for 7 days post vaccination compared with placebo as determined by solicited local and systemic reactogenicity

##### **3.1.2 Secondary Objectives**

To compare the frequency of unsolicited AEs of each dose of TAP-COVID-19 vaccine with CpG adjuvant through Day 43 and SAEs, MAAEs, NOCDs, and AESIs through Day 365

Comparisons include:

- High dose (45 µg TAP-COVID-19 vaccine + 0.5 mg CpG) to placebo
- Low dose (15 µg TAP-COVID-19 vaccine + 0.5 mg CpG) to placebo
- High dose (45 µg TAP-COVID-19 vaccine + 0.5 mg CpG) to low dose (15 µg TAP-COVID-19 vaccine + 0.5 mg CpG)

To evaluate the immunogenicity of TAP-COVID-19 vaccine with CpG adjuvant compared with placebo in terms of antibody assessed by GMTs of both spike RBD IgG and IgM antibodies and neutralizing antibody response, GMFR in neutralizing titer from baseline in all treatment groups at Days 8, 22, 29, 43, 90, 181, 273, and 365 relative to baseline

##### **3.1.3 Exploratory Objectives**

To assess cellular immunity by measuring the numbers of cytokine producing CD4+ and CD8+ T-cells from PBMCs response to vaccine in all treatment groups at Days 8, 22, 29, 43, 90, 181, 273, and 365 compared to baseline

To assess the immunogenicity of the RBD and Fc component of the vaccine

#### **3.2 Endpoints**

##### **3.2.1 Primary Endpoints**

Occurrence of Solicited AEs:

- Solicited administration site reactions (eg, pain, tenderness, erythema/redness, induration/swelling) during the 7-day follow-up period after each vaccination (Day 1-8 and Day 22-29)
- Solicited systemic events (eg, fever, nausea/vomiting, diarrhea, headache, fatigue, myalgia) during the 7-day follow-up period after each vaccination (Day 1-8 and Day 22-29)

### **3.2.2 Secondary Endpoints**

Safety:

- Unsolicited AEs, MAAEs, and AESIs up to Day 43
- SAEs, MAAEs, NOCDs, and AESIs up to Day 365 (approximately 1 year after first vaccination)

Immunogenicity:

- Vaccine ELISA of both RBD IgG and IgM antibodies and neutralizing antibody titers for each treatment group:
  - GMT at baseline and Days 15, 22, 43, 90, 181, 273, and 365
  - GMT ratio ( $GMT_{placebo}/GMT_{TAP-COVID-19}$ ) at baseline and Days 22, 29, 43, 90, 181, 273, and 365
  - GMFR at Days 8, 22, 29, 43, 90, 181, 273, and 365 relative to baseline
  - Seroconversion rates on Days 8, 15, 22, 29, 43, 90, 181, 273, and 365. Seroconversion is defined as the proportion of subjects at the respective time point that have detectable antibodies (IgG and IgM) against SARS-CoV-2 Spike Protein RBD following challenge with vaccine (and potentially by natural asymptomatic or symptomatic infection by the virus in case of a placebo subject).
  - GMI on Days 8, 22, 29, 43, 90, 181, 273, and 365

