- o. Refer to [Table 7-1](#) for a detailed list of clinical laboratory test parameters. Clinical laboratory tests can be repeated once at screening to confirm an out-of-range result. If Part C Expansion (optional) is performed, safety laboratory tests will be performed at screening for all Part C subjects in order to satisfy the inclusion/exclusion criteria. In addition, the first 200 subject in Part C will have safety laboratory tests performed at all time points. The remaining subjects in Part C will not have safety laboratory tests performed at any of the post-dose time points unless the Investigator deems it necessary.
- p. Subjects with positive ELISA anti-N IgG results without COVID-19 symptoms may indicate asymptomatic SARS-CoV-2 infection and will be followed appropriately. Subjects with a positive ELISA anti-N IgG result should have a PCR test and be followed until both are negative as in the protocol instructions ([Section 7.6](#)).
- q. Serostatus will not be used to determine eligibility; however, subjects with a positive serostatus for SARS-CoV-2 will have safety and efficacy subgroup analysis performed.

NOTE: In the event multiple post-dose procedures are required to be conducted at the same nominal time point, the timing of antibody titer and cellular immunity blood sample collections will take priority over all other scheduled activities. In practice, the following order is recommended: (1) vital signs measurements; (2) antibody titer and cellular immunity blood sampling; (3) clinical laboratory tests sampling; (4) physical examination and height and body weight measurements. Vital signs may be conducted up to 10 minutes, prior to the nominal time to minimize the potential autonomic effects of blood draws on these measurements and remaining assessments (eg, clinical laboratory tests sampling, physical examination, and height and body weight measurements) may be performed after the nominal time point.

CONFIDENTIAL

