Prior to receiving a second dose of vaccine, subjects will have the following assessments performed to ensure eligibility: vital signs (including temperature), review of clinical laboratory test results to date, nasopharyngeal swab Day 15 to check for SARS-CoV-2 infection (RT-PCR result must be received by the CRU and negative prior to the second vaccine administration), medical history since last visit including AE assessment for SAEs, Grade 3 AEs, or AESIs that are possibly, probably, or definitely related to study vaccine without a plausible alternative explanation, targeted physical examination, recheck of eligibility criteria, and pregnancy test (as applicable).

Subjects will be monitored for SARS-CoV-2 exposure for potential asymptomatic infection throughout the study.

- If a subject has a positive or borderline ELISA anti-N IgG result, sites should have the subject return for an unscheduled PCR. If the ELISA is positive and the PCR is negative, the sites should follow the subjects using the standard of care under Investigator discretion, retesting ELISA at the next study visit(s) or sooner (per the Investigator's decision).
- If the subject has a positive or borderline ELISA anti-N IgG AND a positive PCR test, the clinical sites should bring the subjects back for repeat PCR testing as described below.
- The clinical sites should continue to collect PCR tests if a subject is experiencing possible COVID-19 symptoms, or had possible exposure to SARS-CoV-2 (ie, close contact tests positive for SARS-CoV-2). Testing will occur every 2 weeks for a total of 4 weeks (if 2 consecutive negative tests) or until negative (x2) after a positive result. Positive results

will be reported as an AESI ([Section 8.2.2](#)) and subjects followed for disease severity, duration, and outcome.

Subjects who are seropositive for SARS-CoV-2 and asymptomatic will be allowed to enroll into Parts A and B of the study as long as the subject is RT-PCR negative.

Additional details for the ELISA test results are presented in [Appendix C](#).

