### **7.5 Immunogenicity**

Blood samples for antibody titers will be collected per [Table 1-1](#) to assess:

- Vaccine (ELISA for IgM and IgG, total antibody) and neutralizing antibody titers (virus microneutralization) for each treatment group:
  - GMT ratio (GMTplacebo/GMTTAP-COVID-19)
  - Seroconversion rate is defined as the proportion of subjects at the respective time point that have detectable antibodies (IgG and IgM) against SARS-CoV-2 Spike Protein RBD following challenge with vaccine (and potentially by natural asymptomatic or symptomatic infection by the virus in case of a placebo subject).
- Anti-RBD and anti-Fc antibodies

Blood samples for cellular immunity (PBMCs) will be collected per [Table 1-1](#). The numbers of cytokine producing CD4+ and CD8+ T-cells from PBMCs responsive to vaccine antigens will be analyzed using a validated procedure.

PBMC and serum samples for future research will also be collected (5-7 aliquots [1 mL]) at the time points outlined in [Table 1-1](#).

Immunogenicity sample collection, processing, and shipping details will be outlined in a separate SRM.

CONFIDENTIAL

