## **9 STATISTICAL CONSIDERATIONS**

The statistical analysis will be conducted following the principles as specified in ICH Topic E9 (CPMP/ICH/363/96).

All statistical analyses will be described in a separate SAP.

The statistical evaluation will be performed using SAS® software version 9.4 or higher (SAS Institute, Cary, NC). All data will be listed, and summary tables will be provided. No formal significance testing will be performed. Summary statistics will be presented by treatment group and include subset analysis (eg, all subjects, seronegative subjects [ie, neutralizing antibody titer < 10 at screening], seropositive subjects, and subjects that received an FDA Emergency Use Authorization/licensed COVID vaccine). For continuous variables, data will be summarized with the number of subjects, mean, standard deviation, median, minimum, maximum, geometric mean, CV%, GeoCV%, and 95% CI by treatment group. For categorical variables, data will be tabulated with the number and proportion of subjects for each category by treatment group.

The database will be locked and unblinded after the data have been monitored for all subjects through Day 43. Details of the unblinded interim analysis are presented in [Section 9.5](#).

The final analysis of the safety and immunogenicity data collected from Day 43 through Day 365/approximately 1 year after first vaccination will be performed after the study is completed. An addendum to the initial CSR will be prepared with data from final analysis. Details of the statistical analyses, methods, and data conventions will be described in the SAP.

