### **9.2 Analysis Populations**

Enrolled Population: All subjects who signed the ICF.

**Safety Population:** All subjects who provide consent, are randomized, and receive any amount of study vaccine/placebo. The Safety Population will be used for the demographic, baseline characteristic, safety data summaries, and the analysis of primary endpoints such as occurrence of solicited local and systemic reactogenicity.

**Per Protocol (PP) Population:** Includes all subjects in the Safety Population who receive the assigned doses of the study vaccine/placebo according to protocol, have serology results, and have no major protocol deviations affecting the primary immunogenicity outcomes, as determined by the Sponsor before database lock and unblinding. Subjects that are immunized with an approved vaccine will be captured as a subset analysis of the PP Population at Days 90, 181, 273, and 365 based on the date of receiving an approved COVID-19 vaccine.

**Modified Intent-to-Treat (mITT) Population:** Includes all subjects in the Safety Population who provide any serology data. The mITT Population will be used for the immunogenicity analysis.

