#### **9.6 Immunogenicity Analysis**

The mITT Population will be used for all listings and summary statistics corresponding to immunogenicity analysis.

The individual sampling and blood collection for ELISA analysis to determine IgG and IgM antibody titers to the spike RBD and neutralizing antibody titers for parent (Wuhan) and any variant SARS-CoV-2 strains, will be listed and summarized by time points for each part by treatment.

All derived immunogenicity secondary endpoint parameters: GMT, GMT ratio, GMFR, GMI, and seroconversion rates will be listed and summarized by scheduled time point using descriptive statistics (n, mean, SD, minimum, median, maximum, geometric mean, CV%, GeoCV%, and 95% CI) for each part by treatment.

PBMC and serum sample data for future research results at each scheduled visit will also be provided separately in a listing and summary table, if applicable.

Subgroup analysis for safety and efficacy will be performed for those subjects who were seropositive when enrolled.

Graphical display of the summary results or at individual time points will be provided as needed (eg, scatter plots of subject titer values to visually display individual data points).

Additional details for analysis of immunogenicity are presented in the SAP.

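### Seroconversion is defined as detectable anti-RBD antibody at the visit, with no baseline condition, so antibody carried in from before the first dose counts as conversion

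*Combined protocol and SAP*

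**What the plan says.** Section 3.2.2 (Secondary Endpoints) gives the rule: "Seroconversion is defined as the proportion of subjects at the respective time point that have detectable antibodies (IgG and IgM") against the spike RBD, "following challenge with vaccine (and potentially by natural asymptomatic or symptomatic infection by the virus in case of a placebo subject"). The synopsis carries the same definition, and section 7.5 repeats it: "Seroconversion rate is defined as the proportion of subjects at the respective time point that have detectable antibodies (IgG and IgM"). The rate is reported at nine visits from Day 8 to Day 365.

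Three other provisions determine who enters that rate:

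- **Eligibility.** Section 4.1 says "Subjects who are seropositive for SARS-CoV-2 and asymptomatic will be allowed to enroll into Parts A and B of the study", provided they are RT-PCR negative, and has a like provision for Part C. Note q to Table 1-1 adds: "Serostatus will not be used to determine eligibility".
- **Population.** Section 9.2 defines the mITT Population: "Includes all subjects in the Safety Population who provide any serology data". Section 9.6 applies it: "The mITT Population will be used for all listings and summary statistics corresponding to immunogenicity analysis".
- **Subsets.** Section 9 plans subset summaries, including "seronegative subjects [ie, neutralizing antibody titer < 10 at screening"]. Sections 9.6 and 9.8 also mention subgroups by serostatus.

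Sections 9 and 9.6 refer further detail to a separate SAP. The text supplied for review contains no SAP rule for seroconversion.

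**The concern.** Seroconversion ordinarily means a change of state, from no detectable antibody to detectable antibody. The definition here looks only at the later of the two time points. In a trial that enrolled only seronegative subjects the two measures would nearly coincide. This trial deliberately admits seropositive subjects and keeps them in the analysis population, so they separate.

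The consequence is a rate that mixes response to the injection with earlier infection. Placebo can show seroconversion without a single new infection. The vaccine rate is raised and the vaccine-placebo gap is reduced. Rates also stop being comparable between Part A and Part B, or between dose cohorts enrolled at different times, if their baseline seropositivity differs.

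No significance test is planned and no decision rule in the protocol uses a seroconversion threshold, so neither type I error nor a stated decision is affected.

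**Working it through.** The plan gives no sample size calculation, no expected seroconversion rate and no baseline seropositivity, so there is no figure of its own to reproduce for this endpoint. The group sizes are internally consistent: 4 cohorts × (30 active + 15 placebo) = 180, which gives 30 placebo subjects per part.

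**Model.** Let *s* be the share with detectable RBD antibody at baseline, and *p* the true conversion rate on vaccine among subjects undetectable at baseline. Both are assumed. I also assume that *s* is equal in the arms, that baseline antibody is still detectable at the visit, that placebo has no new infection, and that one isotype (or either) is counted. Under the written rule:

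- placebo reports *s*
- vaccine reports *s* + (1 − *s*)*p*
- the apparent gap is (1 − *s*)*p*, against *p* among baseline negatives
- expected placebo subjects counted with no new infection, per part: 30*s*
- chance of at least one: 1 − (1 − *s*)^30

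For example, at *s* = 0.10 and *p* = 0.80, vaccine reports 0.10 + 0.90 × 0.80 = 0.82, and the gap is 0.90 × 0.80 = 0.72.

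| *s* | Placebo | Vaccine (*p* = 80%) | Gap (true 80) | Gap at *p* = 50% (true 50) | Placebo counted, of 30 | P(at least one) |
|---|---|---|---|---|---|---|
| 5% | 5% | 81% | 76 | 47.5 | 1.5 | 79% |
| 10% | 10% | 82% | 72 | 45 | 3 | 96% |
| 20% | 20% | 84% | 64 | 40 | 6 | >99% |
| 30% | 30% | 86% | 56 | 35 | 9 | >99% |

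**What remains in the seronegative subset.** That subset is cut on neutralizing titer, whereas the endpoint uses RBD IgG and IgM. A subject with titer below 10 but detectable RBD antibody is labelled seronegative and still counts as converted. If a share *r* of the subset (also assumed) is in that position, the same formulas apply with *r* in place of *s*. At *p* = 80%:

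| *r* | Placebo | Vaccine | Gap (true 80) |
|---|---|---|---|
| 2% | 2% | 80.4% | 78.4 |
| 5% | 5% | 81% | 76 |
| 10% | 10% | 82% | 72 |

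**The joint reading.** If both IgG and IgM must be detectable, carry-over is limited to subjects positive for both at baseline, so *s* is that smaller share. The reported rate is then also capped at the smaller of the IgG-positive and IgM-positive shares. The wording does not settle which reading is meant.

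**The case against.** Five points can be made for the plan.

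1. *The rest of the sentence supplies the condition.* The reference to vaccine challenge, or to infection in placebo, can be read as antibody arising after injection. But it names a cause and gives no testable rule. An assay result at the visit cannot show whether the antibody was already there, and the placebo clause does not say the infection must follow baseline.
2. *The serostatus subsets handle it.* They help. Table 1-1 also schedules an IgM and IgG serostatus test at screening, and note q ties a subgroup analysis to it, so a baseline split on a basis other than neutralizing titer is at least described. However, the assays in Appendix C target spike (IgG) and nucleocapsid (IgG and IgM), and are not the RBD assay behind the endpoint. Section 9 uses neutralizing titer. The all-subject mITT rate remains in either case. Which serostatus rule governs is a further question for the sponsor.
3. *The SAP may hold a baseline rule.* It may, and its absence from the supplied text limits what can be said about the analysis finally run. A rule there would still have to be reconciled with three places in the protocol that state the definition without one.
4. *The figures depend on one reading and on assumed inputs.* That is correct. On the joint reading fewer subjects carry over, and antibody that wanes before late visits reduces the effect there. Amendment 8 also records that enrolment stopped, so achieved numbers may be below 30 per group. The percentages do not depend on that, but the counts and the chances of at least one do.
5. *The endpoint is descriptive.* Also correct. Baseline GMT and GMFR are planned, and under the model above the carry-over would be visible in the placebo rate. These help a careful reader but do not correct the rate itself.

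**Conclusion.** The concern holds. Followed as written, the plan counts RBD antibody already present at baseline as seroconversion, in either arm, for as long as it stays detectable. This is a definition that measures the wrong quantity, and not merely a missing detail.

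Its size depends on baseline RBD positivity, which the documents do not give. Over an assumed 5% to 30%, with 80% true conversion on vaccine, the apparent gap loses between 4 and 24 points. The loss is smaller on the joint IgG-and-IgM reading, where antibody wanes, and probably within the neutralizing-titer subset. The harm is confined to interpretation of a secondary descriptive endpoint, which makes this something the sponsor should fix, without threatening the trial's primary safety objective. Confidence is high about the protocol wording; what the SAP does is unknown from the supplied text.

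**What to change.** In section 3.2.2, section 7.5 and the synopsis:

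- Define seroconversion separately for RBD IgG and RBD IgM, as undetectable at baseline and detectable at the visit on that same assay.
- Set the denominator as subjects undetectable at baseline on that assay who have a result at that visit.
- Report the present measure under the name seropositivity, and include the baseline visit.
- Describe baseline-positive subjects by fold rise, already planned as GMFR.
- If the SAP already has a baseline rule, bring the protocol text into line with it.

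The cost is wording and reprogramming, since anti-RBD blood is already scheduled at screening. Reported rates would fall somewhat and denominators would shrink from the planned 30 per group to about 27 (*s* = 10%) or 24 (*s* = 20%). The loss of precision is small. Exact (Clopper-Pearson) 95% intervals near 80% are:

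| Result | 95% CI | Width (points) |
|---|---|---|
| 24/30 | 61.4% to 92.3% | 30.9 |
| 22/27 | 61.9% to 93.7% | 31.8 |
| 19/24 | 57.8% to 92.9% | 35.0 |

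(Widths are from unrounded limits.)

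Section 6.6.2 unblinds the sponsor at the Day 43 interim analysis. A change made after that point should be disclosed as post hoc, with the rate under the protocol's existing definition shown beside it as seropositivity.
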